We have demonstrated, in rodents (Chierichetti, 2012), and in a large animal [i.e. anesthetized pig with lung injury] model (Yoshida, 2017) that CNAP augments oxygenation and improves compliance, and importantly, it reduces the degree of subsequent lung injury. In the rodent application, the animals developed hypotension, but not in the large animal model. We have recently completed a Phase 1 study on healthy volunteers (HSC REB#1000057680). This demonstrated that the CNAP is well tolerated in awake healthy subjects and caused no adverse effects. Others have used a variation of this approach in anesthetized pigs (Valenza, 2005) and in humans with ARDS (Valenza, 2003), but they did not use recruitment maneuvers; and, the devices used did not encircle the abdomen or achieve effective transmission of negative pressure across the abdominal wall.

In these applications, the approach did not augment ventilation but, neither did they cause any adverse impact.

Finally, the technique has been used (although for a different indication) to reduce elevated intra-abdominal pressure in critically ill patients (Bloomfield, 1999 #247).

Device: A patent (US) application has been filed for the device (owned by SickKids)

RESEARCH OBJECTIVES AND HYPOTHESIS

We wish to perform a safety, 'Phase 2' study in patients that have been diagnosed with Acute Respiratory Distress Syndrome (ARDS) to determine primary safety and efficacy of using CNAP.

Safety (Stop rules)

↓mean arterial pressure <60 mmHg or ↓15%
(despite 500 mL fluid or increase norepinephrine)
↓SpO2 (drop >5%)
↓PaO2/FiO2 >20% .

Efficacy ↑PaO2/FiO2 >20%

RECRUITMENT PROCESS

Patients will be recruited from the Intensive Care Unit, following completion of informed consent from the patient or legally authorized substitute decision maker (SDM) (see Consent Form). Please see "Inclusion and Exclusion criteria"

POPULATION TO BE STUDIED

Patients with ARDS. Weight range 40-100 kg. Ventilated with positive pressure ventilation and a P/F ratio ≤200 mmHg with PEEP ≥5 cmH2O

Inclusion Criteria:

- 1) Patients ≥ 18 years old
- 2) Patients with moderate to severe ARDS as per the Berlin definition (PaO2/FiO2 ≤200mmHg) (Ranieri, 2012)
- 3) Patients with absence of any significant cardiopulmonary disease

Exclusion Criteria:

- 1) Contraindication to CNAP
 - a. open abdominal wounds or drainage tubes
 - b. Acute brain Injury with intracranial pressure >30 mm Hg or cerebral perfusion pressure <60 mmHg

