 - c. Decompensated heart insufficiency or acute coronary syndrome
 - d. Major hemodynamic instability: Mean arterial pressure lower than 60 mm Hg despite adequate fluid resuscitation and two vasopressors or increase of vasopressor dose by 30% in the next 6 hours.
 - f. Unstable spine, femur, or pelvic fractures
 - g. Pregnancy
 - h. Pneumothorax
- 2) Contraindication to EIT electrode placement
Burns, chest wall bandaging limiting electrode placement
- 3) Severe liver insufficiency (Child-Pugh score > 7) or fulminant hepatic failure
- 4) Major respiratory acidosis or PaCO₂ > 60 mmHg
- 5) Severe COPD (according to the GOLD criteria defined as severe = FEV1: 30-50% or very severe = FEV1 < 30%)
- 6) Clinical judgement of the attending physician

INTERVENTIONS AND RESEARCH PROCESS

Pre-Human Testing: The device has been extensively tested (the first prototype was successfully tested on a pig with good success (Yoshida, 2017).

The current device has undergone a closed loop stress test for 24 hours (-10 cmH₂O) and showed no signs of failure. This device was made in the laboratory of [name] in the department of Biomedical Engineering.

The device has also been tested on a Mannequin (please see photograph in the appendix), with no leakage.

Protocol (summarized in Flow Chart):

- 1) Eligible patients will be identified with research coordinators by daily screening in the intensive care unit
- 2) Consent for participation will be obtained from the patient's substitute decision maker
- 3) Prior to starting the application of CNAP, patients will be sedated deeply with sedatives and/or opioids, and will be paralyzed with a continuous infusion of rocuronium, if not started (7 µg/kg/min).
- 4) Also we will install the EIT to visualize the ventilation pattern.
- 5) Baseline measurement (see Appendix, ARDS Registry Form)

- a) Lung Mechanics
- b) Pressure-Volume Curve,
- c) determination of Recruitability, and
- d) Fluid Responsiveness.

6) Stage 1

the CNAP device is attached to the abdomen (but no suction), and a complete set of vital signs recorded.

7) Stage 2

a suction is applied to the CNAP device until chamber pressure will reach -5cmH₂O, and vital signs carefully monitored. If no impact, go to stage 3.

8) Stage 3

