the suction level will be increased until esophageal pressure will decrease by -3cmH₂O, as per the primary team, and vital signs recorded. If no impact, go to next stage after discuss with the clinical team and attending physician responsible for the patient's care

9) Stage 4 & 5

First, lung recruitment with CPAP 40cmH₂O for 10sec. Then the suction will be applied until esophageal pressure will decrease by -3cmH₂O, as per the primary team, and vital signs recorded.

10) Stage 6

when the study is finished, and the device removed, monitoring will continue –along with primary team- as per usual ICU care.

At each stage, if any concern (Safety-Stop rules, see above), the primary care team will immediately stop the CNAP. If effective (Efficacy, see above), CNAP will continue for 2 hours.

If the device appears to have helped, it can (at the request of the care team) be left in place for a total of 24h.

A SCHEMATIC of the study protocol is appended (Flow chart).

The following parameters will be recorded (see Flowchart & Case report form).:

Hemodynamic (S/M/DAP, HR, CVP)

Respiratory Mechanics (RR, VT, mPaw, PIP, Pplat, PEEP, end-exp. Pes, EIT)

Gas Exchange (FiO₂, SpO₂, PaO₂, PaCO₂)

Abdominal Pressure (Pbladder)

ANTICIPATED OUTCOME

We anticipate no significant impact on cardiovascular physiology; we expect some improvement of the P/F ratio, lung compliance and ventilation distribution.

SAMPLE SIZE AND JUSTIFICATION

A convenience sample size of 20 patients will be invited to participate. We anticipate that patient oxygenation will increase with CNAP application in conjunction with positive pressure ventilation vs positive pressure ventilation alone.

Because we will use sensitive markers of any impact on respiratory or circulator parameters (including patient reported dyspnea, and key parameters (see Data Sheet), this will facilitate detection of any potentially adverse effects.

RESEARCH PROCEDURES

Analysis will consist of inspection of the data associating transition to and withdrawal from CNAP.

We estimate that the total time in the CNAP device might be around 6 hours, but it could take less time or more time. Throughout this period, close monitoring will ensure comfort and safety.

SAFETY PROCEDURES

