The testing will be performed beside in the Intensive Care Unit at St Michael's Hospital. A staff physician will be present, and dedicated to monitoring the subject and ensuring safety. No medications will be administered. All data will be digitized and securely stored.

DEFINITION AND MEASUREMENTS

Demographic Data: Demographic data will be obtained from the patient's medical file: Age, gender, height and weight, Admission diagnosis, Cause of acute respiratory failure, Significant comorbidities (COPD, CHF, other chronic organ insufficiency), Days on ICU and days on MV (days), APACHE II severity score and SOFA score on the day of the test, etc (See case report form).

Electric Impedance Tomography: EIT data will be recorded using the PulmoVista®500 (Dräger, Lübeck, Germany) with 16-electrode silicon belt, placed on the perimeter defining a cross sectional plane of the thorax at the level of the 5th intercostal space (parasternal line). In all patients, EIT data will be recorded at each stage, and analyzed with the dedicated analysis tool (Dräger EIT analysis Tool 6.1). EIT images will be divided into two (and four) zones, each covering 50% (and 25%) of the ventro-dorsal direction, for the analysis of ventilation pattern.

Airway Pressure, Esophageal Pressure and Flow: The esophageal balloon (Copper Surgical, Trumbull, CT, USA) will be inflated by 1.0 ml of air volume. If applicable, we will record the data as follows (if not applicable, we will record the data from the ventilator monitor and portable monitor). The proximal end of the catheter is connected to a pressure transducer and recording equipment (MP150; Biopac systems, Goleta, CA,

USA). Airway flow and pressure sensors will be connected to the respiratory circuit, proximal to the Y-piece. The flow will be measured through a pneumotachograph (Fleish No. 2; Metabo; Epalinges, Switzerland) adequately calibrated using a 1 L syringe to obtain integration of 1 L equals to 1 Volt. Proximal airway pressure will be measured using a differential pressure transducer (TSD160series: Biopac systems, Goleta, CA, USA) previously calibrated at 10 and 0 cmH₂O using a water column. Signals will be acquired with an analogue-digital converter (MP150; Biopac systems, Goleta, CA, USA), sampled at 200 Hz and stored in a laptop computer for subsequent off-line analysis (Acqknowledge 4.3, Biopac Systems).

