- 1) Transpulmonary pressure (PL): Maximal values of PL = [airway pressure – esophageal pressure] will be recorded as peak PL. We also will calculate Δ PL as the difference between the airway driving pressure and Δ esophageal pressure (i.e. airway pressure – PEEP – Δ esophageal pressure) corresponding to the same time phase and we will pick up the maximal value as peak Δ PL. Plateau PL will be calculated as [airway pressure - esophageal pressure] after making an inspiratory hold (i.e. zero flow phase). Expiratory PL will be calculated as [airway pressure - esophageal pressure] after making an expiratory hold.
- 2) Airway pressure and flow: Plateau pressure, peak airway pressure and PEEP will be measured, as previously described (Henderson, 2017). Tidal volume will be calculated as integral of flow. Considering the total stretching pressure across respiratory system (lung + chest wall) with spontaneous breathing during mechanical ventilation, driving pressure will be calculated as the sum of [plateau pressure – PEEP] and the changes in esophageal pressure corresponding to plateau phase when compared with passive conditions (Yoshida, 2013). During muscle paralysis, driving pressure was calculated as [plateau pressure – PEEP]. The dynamic compliance of the respiratory system was defined as: [VT/ driving pressure].

Hemodynamics: Arterial blood pressure and heart rate will be continuously monitored on the ICU bedside monitor.

Arterial Blood Gas: pH, PaCO₂, PaO₂ will be measured by standard clinical technique using the ICU blood gas analyzer.

STATISTICAL ANALYSIS

Statistical analysis will be performed using standard software SPSS13.0 for Windows (SPSS, Chicago, IL, USA). The results are expressed as mean \pm standard deviation. 1-way analysis of variance for repeated measures will be used to evaluate the impact of time. In the post hoc analysis to separate differences between the means, a Tukey's pair-wise multiple comparison test will be used. All tests were two-tailed, and differences were considered significant when $p < 0.05$

REFERENCES

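### Fluid or norepinephrine given during the CNAP stages would bias the stage comparison of MAP toward no change, and no stated analysis takes that support into account

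*Combined protocol and SAP*

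**What the plan says.** - **Research Objectives and Hypothesis, Safety (Stop rules).** The MAP criterion is "mean arterial pressure <60 mmHg or ↓15"%, qualified by "despite 500 mL fluid or increase norepinephrine".
- **Exclusion Criteria, 1d.** Patients are excluded for "Mean arterial pressure lower than 60 mm Hg despite adequate fluid resuscitation and two vasopressors", or for a vasopressor dose rising by 30% over six hours. A patient whose pressure is steady on a steady vasopressor dose is not excluded by this item.
- **Interventions and Research Process, list of parameters.** "The following parameters will be recorded (see Flowchart & Case report form"), followed for the circulation by "Hemodynamic (S/M/DAP, HR, CVP"). Neither vasopressor dose nor fluid given is on the printed list.
- **Anticipated Outcome.** "We anticipate no significant impact on cardiovascular physiology".
- **Statistical Analysis.** "1-way analysis of variance for repeated measures will be used to evaluate the impact of time", with Tukey comparisons, two-sided at 0.05. No outcome variable, covariate or rule for support is named.
- **Safety Procedures.** "No medications will be administered".

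**The concern.** Safety is a stated aim of the study, and the background reports hypotension in the rodent work, so the circulatory result matters. Once a clinician gives fluid or raises norepinephrine in response to a falling pressure, the recorded MAP reflects CNAP plus treatment. The effect of CNAP is then divided between the remaining fall in MAP and the extra support. A test of MAP across stages sees only the first part.

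The loss is greatest in the patients who reacted most, because they are the ones most likely to be supported. A flat MAP profile could then be read as confirming the anticipated absence of cardiovascular impact when treatment had partly produced it. This point is about the comparison of MAP between stages. It is not about which falls should count as stop events.

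**Working it through.** **1. Nothing to reproduce.** The 20 patients are a convenience sample. The plan gives no effect size, SD or power for MAP, so every clinical value below is an assumption. Only n = 20, the two-sided 5% level, the choice of test and the stop-rule threshold come from the documents.

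**2. Simple model.** Assume a true mean fall of 8 mmHg and an SD of the paired change of 8 or 10 mmHg. Assume also that 40-80% of patients are supported and that 75-100% of their fall is restored.

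Observed fall = true fall × (1 − share supported × share restored)

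- Mildest: 8 × (1 − 0.40 × 0.75) = 5.6 mmHg
- Middle: 8 × (1 − 0.60 × 1.00) = 3.2 mmHg
- Worst: 8 × (1 − 0.80 × 1.00) = 1.6 mmHg

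Power comes from the noncentral t with 19 degrees of freedom (critical value 2.093) and noncentrality = observed fall × √20 / SD. With no support and SD 8, this is 8 × 4.472 / 8 = 4.47.

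| Observed fall (mmHg) | Noncentrality, SD 8 / SD 10 | Power, SD 8 / SD 10 |
|---|---|---|
| 8.0 (no support) | 4.47 / 3.58 | 99% / 92% |
| 5.6 | 3.13 / 2.50 | 84% / 66% |
| 3.2 | 1.79 / 1.43 | 40% / 27% |
| 1.6 | 0.89 / 0.72 | 14% / 10% |

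**3. The planned test.** The one-way repeated-measures ANOVA was simulated with n = 20, five stages and 1,500 runs per setting. The assumed fall was 8 mmHg at Stages 3-5 and half that at Stage 2, with a within-patient SD of 8. Power is 90% with no support, 31% if half the fall is restored, 8% if 80% is restored, and 5% (the type I error) if all is restored.

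**4. Support tied to the stop-rule threshold.** Here half the patients are assumed to fall by 15 mmHg from a mean baseline of 75 mmHg, and MAP is assumed to return to its Stage 1 level once the threshold is crossed. ANOVA power drops from 94% to 6%, and Tukey detection of any fall from 92% to 1.5%, although about 59% of patients cross the threshold. With 30% of patients affected, ANOVA power drops from 60% to 6.5%.

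**5. What counting support would show.** Take as a patient-level outcome that the MAP stop rule was met or support was started or increased. For 0 of 20 the exact 95% upper limit is 1 − 0.025^(1/20) = 16.8%. For 4 of 20 the interval is 5.7 to 43.7%, and for 8 of 20 it is 19.1 to 63.9%. The chance of seeing at least one such patient is 1 − 0.90^20 = 87.8% if the true share is 10%, and 1 − 0.80^20 = 98.8% if it is 20%.

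**The case against.** A reader might infer that the plan titrates norepinephrine to hold MAP, tests MAP alone, and fails to collect doses. The documents do not support that reading.

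- **Support is allowed, not prescribed.** The stop rule only qualifies when a fall counts. No MAP target or routine titration is described, and Safety Procedures says "No medications will be administered". That sentence contradicts the stop rule, and also the rocuronium infusion in the protocol steps. It therefore cannot settle whether support will be given, and the passages must be reconciled.
- **The record may be complete.** The printed list points to a flowchart and case report form that are not available. Exclusion 1d already uses vasopressor dose, so collection is plausible. A gap can be shown only in the printed list.
- **The Statistical Analysis section names no variable.** That MAP will be tested without regard to support is inferred from an ANOVA whose only factor is time.
- **There is some protection.** Arterial pressure and heart rate are monitored continuously, CVP is recorded, and Research Procedures foresees inspecting the data around transition to and withdrawal from CNAP. An acute fall could be seen there.
- **The sizes are not anchored.** The simple model treats support as unrelated to the size of the fall and keeps the SD fixed. With the same fall and SDs and an assumed baseline MAP of 70-85 mmHg, about 28-42% of patients would cross the threshold. That is at or below the bottom of the assumed 40-80%.

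All of this stands as a limit on how strongly the point can be put. It does not remove the point. The stop rule foresees support, and no stated analysis uses it wherever it is recorded. Inspection of the data has no rule for support either. The threshold model in step 4 of the working masks the effect as well, so the direction does not depend on the simple model.

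**Conclusion.** The point holds in conditional form. If fluid or norepinephrine is given during the stages, the stage MAP comparison is biased toward no change, and a conclusion of no cardiovascular impact could partly reflect treatment. The direction follows from the plan's own stop rule. The size is illustrative only: under the stated assumptions, power falls from 92-99% to anywhere between 84% and 10%. How often support would be used is unknown, so masking is possible rather than certain. It would be wrong to say that doses are not collected, or that the plan commits to holding MAP at a target.

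This should be changed. The correction is cheap, and it affects what the study can say about a primary safety question.

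**What to change.** 1. Record norepinephrine dose and cumulative fluid at each stage, if the case report form does not already do so.
2. Report their paired changes from Stage 1 beside the change in MAP.
3. Report the number of patients who met the MAP stop rule or had support started or increased during CNAP, with an exact 95% confidence interval.
4. Word any statement on cardiovascular impact from the confidence intervals for MAP and support together. A non-significant MAP test in 20 patients is not evidence of no impact.
5. Do not use the last MAP before support as the main stage value. Support begun at one stage carries over into later ones, and the rule selects low readings. Simulations with no CNAP effect, under assumed values, gave a spurious fall of 0.4 to 1.8 mmHg and a type I error of 6 to 13%. If it is used, make it a sensitivity analysis with both biases stated.
6. Reconcile the Safety Procedures statement on medications with the stop rule and the protocol steps.

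The cost is two fields taken from the ICU chart and one extra table. No change to patient care is proposed.

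### Improved lung compliance is expected, but the only compliance defined is that of the whole respiratory system, which includes the chest wall

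*Combined protocol and SAP*

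**What the plan says.** Under ANTICIPATED OUTCOME the investigators write: "we expect some improvement of the P/F ratio, lung compliance and ventilation distribution". The compliance named there is that of the lung.

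DEFINITION AND MEASUREMENTS, item 2 (airway pressure and flow), holds the only compliance formula in the text: "The dynamic compliance of the respiratory system was defined as" tidal volume divided by driving pressure. Driving pressure takes two forms:

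- With spontaneous breathing, it is plateau minus PEEP plus "the changes in esophageal pressure corresponding to plateau phase when compared with passive conditions".
- In passive patients: "During muscle paralysis, driving pressure was calculated as" plateau minus PEEP.

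The sentence that introduces driving pressure opens with "Considering the total stretching pressure across respiratory system (lung + chest wall", so the plan itself treats this pressure as acting on both structures. Step 3 of the protocol list (INTERVENTIONS AND RESEARCH PROCESS) says that, before CNAP starts, patients "will be paralyzed with a continuous infusion of rocuronium". The passive form is therefore the one in use.

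Item 1 (transpulmonary pressure, PL) supplies lung-specific quantities: "We also will calculate Δ PL as the difference between the airway driving pressure and Δ esophageal pressure", kept as its maximum; plateau PL, taken at an inspiratory hold; and expiratory PL, taken at an expiratory hold. Nowhere is tidal volume divided by any of these.

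Two further places matter. The list of recorded parameters that closes the protocol steps names esophageal pressure (Pes) at end-expiration only. The paragraph on airway pressure, esophageal pressure and flow makes the full signal acquisition conditional, with ventilator and portable-monitor readings as the fallback.

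**The concern.** The expectation concerns the lung, but the formula concerns lung and chest wall in series. CNAP is applied to the abdomen, so the chest-wall side is where a direct mechanical effect is plausible. If suction changes how much esophageal pressure rises during a tidal breath, respiratory-system compliance changes with the lung unaltered. A real gain in the lung could equally be offset. On this measure alone, the expectation of better lung compliance could be neither supported nor refuted.

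The label adds a smaller difficulty. A plateau is read at zero flow, so a plateau-based ratio is quasi-static. Calling it dynamic invites a reader to assume that peak airway pressure was used.

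**Working it through.** The plan gives no compliance value, tidal volume or pressure to reproduce. The check is therefore algebra, followed by an illustration on assumed values.

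**Algebra.** At zero flow in a passive patient, plateau − PEEP = ΔPL + ΔPes, where ΔPL = plateau PL − expiratory PL and ΔPes is the tidal esophageal swing. Then:

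- respiratory system: Crs = VT/(ΔPL + ΔPes), which is the plan's formula
- lung: CL = VT/ΔPL
- chest wall: Ccw = VT/ΔPes
- hence 1/Crs = 1/CL + 1/Ccw

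**A uniform shift cancels.** The suction target in Stages 3 to 5 is a 3 cmH2O change in esophageal pressure. If Pes falls by 3 at both holds, for example from 10 and 14 to 7 and 11 cmH2O (assumed), the swing is 4 before and after. Only a change in the swing itself matters for this point.

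**Assumed inputs.** VT 400 mL, PEEP 10, plateau 25 and peak airway pressure 32 cmH2O; ΔPes 2, 4 or 6 cmH2O. So plateau − PEEP = 15, ΔPL = 13, 11 or 9, and Crs = 400/15 = 26.7 mL/cmH2O in all three cases.

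| ΔPes | CL = 400/ΔPL | Ccw = 400/ΔPes | Crs if Ccw × 0.7, CL fixed | Crs if Ccw × 1.5, CL fixed |
|---|---|---|---|---|
| 2 | 30.8 | 200.0 | 25.2 (−5.4%) | 27.9 (+4.7%) |
| 4 | 36.4 | 100.0 | 23.9 (−10.3%) | 29.3 (+9.8%) |
| 6 | 44.4 | 66.7 | 22.8 (−14.6%) | 30.8 (+15.4%) |

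Example for the last row: Ccw × 1.5 makes the swing 6/1.5 = 4, so Crs = 400/(9 + 4) = 30.8.

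**Masking.** Suppose CL truly rises by 20%, so ΔPL becomes 10.83, 9.17 or 7.5. With Ccw fixed, Crs rises by 16.9%, 13.9% or 11.1%. The gain disappears from Crs if Ccw falls to 0.48, 0.69 or 0.80 of its baseline. For ΔPes 6: 7.5 + 6/0.80 = 15, the starting value.

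**Label.** With the same inputs, a ratio using peak pressure is 400/(32 − 10) = 18.2, against 26.7 by the plan's formula.

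**Can lung compliance be recovered from what is listed?** Plateau PL and ΔPes both need Pes at the inspiratory hold. The definitions call for it, but the recording list does not include it. The maximal ΔPL does not fill the gap: it is not stated to be taken at zero flow, so VT divided by it would not be a quasi-static lung compliance.

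**The case against.** The best defence is that the plan already contains the parts: tidal volume, both holds and an esophageal balloon. Baseline lung mechanics and a pressure-volume curve are also listed. The registry form, flow chart, data sheet and case report form are cited but are not in the text available here, and they may name lung compliance. A reader might infer that lung compliance will never be computed. The documents do not support that; they show only that the available text does not define it.

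A reader might also infer that a rise in the defined measure would be reported as better lung compliance. No sentence says so. The measure is labelled as belonging to the respiratory system, and recruitment would also be judged on impedance tomography, transpulmonary pressures and P/F.

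The opposite inference, that every input is already secured, does not stand either, given the end-expiratory-only recording list and the conditional acquisition.

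Two further objections hold in part. The documents do not say whether CNAP changes chest-wall compliance at all, so the percentages show what is possible, not what is expected. And relabelling alone would change no result, because the formula is explicit.

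What remains is that the expectation and the only formula refer to different quantities, and that the recording list as written would not allow the right one to be calculated.

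**Conclusion.** The point holds as a mismatch between the stated expectation and the defined measure. In the illustration, a chest-wall change alone, by a factor of 0.7 to 1.5, moves respiratory-system compliance by about −5% to +5% at a swing of 2 cmH2O and about −15% to +15% at a swing of 6. Those figures rest wholly on assumed volumes and pressures, and on a changed tidal swing rather than a uniform fall in esophageal pressure.

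Use of the passive formula rests on the paralysis step. SAFETY PROCEDURES says that no drugs will be given, and the two statements must be reconciled. The conclusion does not depend on the answer, because both forms of driving pressure relate to the whole respiratory system.

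The consequence is moderate. Lung compliance is one of three expected physiological benefits. The stated efficacy criterion is a rise in PaO2/FiO2 of more than 20%, and the 20 patients are a convenience sample; neither depends on compliance.

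**What to change.** 1. Define lung compliance as VT/(plateau PL − expiratory PL), from the inspiratory and expiratory holds already planned, and use it for the lung-compliance expectation.
2. Report chest-wall compliance, VT/ΔPes at the same holds, and respiratory-system compliance beside it, so that the source of any change can be seen.
3. Rename the existing measure quasi-static respiratory-system compliance.
4. Reconcile the list of recorded parameters with the transpulmonary definitions by adding end-inspiratory Pes at the hold. This has to be done before data collection, because a value not recorded cannot be recovered.
5. State how many patients contribute to lung compliance at each stage.

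The cost is a few lines of text and one extra recorded value per stage. The drawback is that lung compliance will be missing where the full esophageal recording is not applicable; respiratory-system compliance would still be available for those patients from ventilator readings.

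### Safety is a primary aim defined by per-patient stop rules, but no count, proportion or interval of patients meeting them is planned

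*Combined protocol and SAP*

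**What the plan says.** The objective in Research Objectives and Hypothesis is "to determine primary safety and efficacy of using CNAP". Under Safety (Stop rules), the same section sets numeric limits for a fall in mean arterial pressure (MAP), with the qualifier "despite 500 mL fluid or increase norepinephrine", for a drop in SpO2 and for a fall in PaO2/FiO2. A rise in PaO2/FiO2 of more than 20% is the efficacy criterion. Each is a yes/no outcome for a patient.

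Interventions and Research Process applies the rules during the staged procedure: "At each stage, if any concern (Safety-Stop rules, see above), the primary care team will immediately stop the CNAP". At Stage 1, "the CNAP device is attached to the abdomen (but no suction), and a complete set of vital signs recorded". Suction starts at Stage 2, with the instruction "If no impact, go to stage 3". For responders, "If effective (Efficacy, see above), CNAP will continue for 2 hours".

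Statistical Analysis gives means with standard deviations, then "1-way analysis of variance for repeated measures will be used to evaluate the impact of time", Tukey pairwise comparisons, and two-sided significance at p < 0.05. Research Procedures adds inspection of the data around going on to and coming off CNAP. Sample Size and Justification describes 20 patients to be invited, as a convenience sample, with no power or precision statement.

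**The concern.** The safety aim asks how many patients meet a stop rule. The formal analysis asks whether the average changes over time. A few large falls among many stable patients barely move an average, so the analysis could be followed exactly without producing a stop-rule rate or any measure of its uncertainty.

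A second gap follows from the staging. A patient whose CNAP is stopped early cannot supply on-suction values at later stages. The plan does not say how those empty stages are handled. A conventional repeated-measures ANOVA uses only patients with every stage, so run that way it would leave out patients stopped for safety.

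At stake is the main safety statement of the study. Without a count, a denominator and an interval, readers cannot judge what a result from at most about 20 patients rules out.

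**Working it through.** **The plan's own figure.** The sample of 20 has no effect size, event rate, power or precision behind it, so there is nothing to reproduce.

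**Inputs from the protocol.** n = 20 (Sample Size and Justification); the 15% MAP fall (Safety, Stop rules). **Assumed:** 3 patients have such a fall, with the fluid/norepinephrine qualifier met, and 17 have no change.

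**1. Effect on the mean.** Mean fall = (3 × 15% + 17 × 0%) / 20 = 45/20 = 2.25%. With falls of 20% it is 60/20 = 3.0%.

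**2. What a test of means would make of it.** For one stage against baseline, let each of the 3 falls have size d. The mean is 0.15d, and the sample SD is d × √(20 × 0.15 × 0.85 / 19) = 0.366d. The standard error is 0.366d/√20 = 0.0819d, so t = 0.15/0.0819 = 1.83 on 19 degrees of freedom, p = 0.083. The size d cancels, so the answer is the same however large the falls. This is a single paired comparison on idealised data, not the full ANOVA. It shows only that a 15% stop rate can go with a non-significant test of means.

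**3. The same data as events.** Exact (Clopper-Pearson) two-sided 95% intervals:

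| Events | Proportion | 95% CI |
|---|---|---|
| 0/20 | 0% | 0 to 16.8% |
| 1/20 | 5% | 0.1 to 24.9% |
| 2/20 | 10% | 1.2 to 31.7% |
| 3/20 | 15% | 3.2 to 37.9% |

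For zero events the upper limit is 1 − 0.025^(1/n). Twenty patients are to be invited, so fewer may be treated: n = 18 gives 18.5% and n = 15 gives 21.8% (both n assumed).

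**4. Stages not reached.** Suppose k of the 3 patients are stopped before the last suction stage and the analysis is complete-case. The mean fall at that stage is (3 − k) × 15% / (20 − k):

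- k = 0: 45/20 = 2.25%
- k = 1: 30/19 = 1.58%
- k = 2: 15/18 = 0.83%
- k = 3: 0/17 = 0%

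This shows what could happen if only safety stops caused missing stages. The protocol does not settle that: a patient who meets the efficacy criterion may also be held at a stage, which would remove responders from later stages as well.

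**The case against.** - **ANOVA is not the only analysis mentioned.** That is true. Inspecting the data around withdrawal of CNAP can take in safety stops. It is informal, however, and names no count, denominator or interval.
- **The misuse is not in the plan.** A reader might infer that a non-significant ANOVA will be offered as proof of safety, especially beside "We anticipate no significant impact on cardiovascular physiology". The documents do not support that: the sentence is an expectation, not a decision rule. What stands is that the named test could not show safety.
- **The missing-stage point is inferred.** A reader might conclude that stopped patients will be dropped and that CNAP will therefore look safer than it is. The documents do not say that the ANOVA is complete-case or that its time factor is the suction stage. Monitoring continues after device removal. Responders may also miss stages, so the direction of any bias is unknown. What stands is that handling is not stated.
- **Some material is not in the supplied text.** The flow chart, data sheet, case report form and registry form may describe recording after a stop. Absence can be claimed only for the supplied text. Still, the statistical section does not refer to any of them for a safety tabulation.
- **The example is constructed.** This is correct. Three fallers and 17 unchanged patients is an assumption. The exact intervals depend only on the counts and the number of patients.
- **This is a small convenience sample.** That argues for simple counts with exact intervals rather than against them.

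**Conclusion.** The concern holds in this form: safety is a primary aim defined by per-patient rules, and the supplied text plans no count, proportion or interval of patients meeting them. It should be fixed, and cheaply. On the stated assumptions, a 15% stop rate appears as a 2.25% mean fall. Even a result with no events leaves a true rate of up to 16.8% compatible with the data at n = 20. The parallel efficacy criterion has the same gap, since no responder proportion is planned.

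The textual gap is firm. The loss of stopped patients from the ANOVA is a possibility that the plan leaves open. It is also not shown that safety events would go unnoticed: the rules are applied at the bedside and vital signs are recorded. What is missing is how the events are summarised.

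One separate matter does not bear on this conclusion. Sample Size and Justification relies on dyspnoea reported by patients, while Interventions and Research Process has patients deeply sedated and paralysed before CNAP. Those passages must be reconciled.

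**What to change.** 1. **Main safety result (Statistical Analysis).** Report the number and proportion of patients meeting any stop rule, and each rule exactly as written, among all patients who started suction, with exact 95% confidence intervals and a listing by stage. List separately any event at Stage 1, when the device is on without suction, and any stop for a concern outside the numeric rules. Name one pre-suction reference value for percentage falls and use it throughout. Report the proportion meeting the efficacy criterion in the same way.
2. **Comparison of means.** Keep it as a secondary analysis. State how many patients contribute at each stage and why others do not. Use all available values, including the one that led to a stop, for example in a mixed model with a simple covariance. A baseline and six stages would be 7 occasions, and an unstructured covariance would need 7 × 8/2 = 28 parameters from about 20 patients. State the model's assumption that, given the recorded values, unreached stages are missing at random.
3. **Precision (Sample Size and Justification).** State that 0/20 events has a two-sided 95% upper limit of 16.8% (18.5% for 0/18, 21.8% for 0/15).

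The cost is protocol wording and a little more analysis. MAP, SpO2 and blood gases are already to be recorded; the case report form may need a line for the rule met and the stage, if it does not have one. The price is a more modest safety claim.
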